**Overview**

For Aim 5 80 (ages 25-65) Gold 0-2 subjects that are current smokers (defined by PFTs, questionnaires and interviews as discussed below) will be recruited. Participants will be equally distributed between males and females and will be representative of the national racial/ethnic populations. Subjects will be recruited using advertisements, email blasts, smoking cessation clinic and physician referrals. Participants that are enrolled into the study will have a total of 4 visits (baseline, 30 day, 60 day and 90 day) over 3-4 months. During the study visits, subject will have vitals, blood tests, urine sample, CT scans, pulmonary function tests, and complete questionnaires. Subjects will also participate in a smoking cessation program. Subjects will be contacted weekly, by phone, for smoking cessation follow up.

**Inclusion/exclusion criteria**

Inclusion criteria
Between the age of 25 to 65 at baseline
Be willing to participate in a smoking cessation program
Be willing to attend all clinic visits
Must be currently smoking at least ½ pack/day at baseline (confirmed with cotinine level and CO Smokerlyzer
>5 pack-year history of smoking
GOLD 0: FEV1≥0.80 and FEV1/FVC>0.70
GOLD 1: FEV1≥0.80 and FEV1/FVC < 0.70
GOLD 2: 0.50≤FEV1<0.80 and FEV1/FVC < 0.70
Be willing to abstain from using any nicotine patches, e-cigarettes, or marijuana for the duration of the study.
Exclusion criteria
Women only: Cannot be pregnant or nursing at baseline or plan to become pregnant during the course of the study
Body Mass Index (BMI) > 32
Weight > 220 pounds
Allergies to shell fish, seafood, eggs or iodine
Heart disease, kidney disease or diabetes
Diagnosis of asthma
Any metal in or on the body (that cannot be removed) between the nose and the abdomen
Any major organ system disease (by judgement of the study medical team)
A glomerular filtration rate of 60 cc per minute or less.
Nitroglycerin usage or nitrates and use of PDE5 inhibitors

Prior history of hypersensitivity to sildenafil
Currently prescribed a phosphodiesterase (PDE) inhibitors medication (ex: Viagra, Cialis, etc)
Known Pulmonary Hypertension
Has used e-cigarettes and marijuana <1 years

**Recruitment**

Subjects will be recruited using IRB approved advertisements and subjects will also be referred to our study by physician teams and the UIHC smoking cessation clinics. We will also notify, by phone or letter, subjects enrolled in the COPDGene IRB: 200710717 and Spiromics IRB: 201308719 studies, who have consented to be contacted for other studies they may qualify for.

**Pre-Screening**

When potential subjects call or are contacted, they will be given information about the study, its procedures and time commitment. If the subject is interested, the subject will be pre-screened using the IRB approved form. If subject appears to qualify, a study visit will be scheduled.

**Consent**

Subjects will be consented in a private room and given time to read through the Informed Consent document if they have not already done so. They will be given time so that the study team can answer any questions they might have regarding the study privately. The study team member will then go through the consent form to verify that the subject understands what to expect, what is involved with the study, what the risks are, confidentiality and privacy aspects, etc. Once the study team member is confident that the candidate understands and is comfortable with participating in the study and the study team has answered all the subject's questions, the study team member will have the subject sign and date the consent form. The study team member who is performing the consent will also sign and date the consent form and make sure the subject has a copy of it for their own files before they leave.

**Schedule of Study Assessments and Procedures**

Activity	Consenting visit	Baseline visit	30 day visit	60 day visit	90 day visit
Written Informed Consent	X	X			
Pre-screen Inclusion/Exclusion form	X	X			
Human Subject Questionnaire		X			
St. George's Respiratory Questionnaire		X			X
Chronic Respiratory Questionnaire		X	X	X	X
Baseline Dyspnea Index Questionnaire		X	X	X	X
Medication review		X	X	X	X
Fagerstrom Questionnaire		X			
Tobacco Interview Form		X			
Six Minute Walk Test w/BORG Scale		X			X
Vitals		X	X	X	X
Height & weight		X			
Exhaled CO Smokerlyzer		X	X	X	X
Pulmonary Function Tests a		X			X
IV Catheter placement		X			X
Blood draw for serum creatinine		X			X
Blood draw for serum cotinine		X	X	X	X
Blood draw for C-reactive protein level		X			X
Blood draw for serum and plasma		X			X
Urine pregnancy test in WOCBP		X	X	X	X
Urine sample for bio specimen collection		X			X
Contrast perfused blood volume (PVC) CT scan b		X			X
Non-contrast CT scan		X	X	X	X
Smoking cessation enrollment		X			
Smoking cessation in person follow-up**			X	X	X
Review and record any SAE/AE or medication changes			X	X	X
Dispense medication/placebo		X	X	X	

**\*\*Subject smoking cessation follow-up phone calls will be done once per week by study coordinator while subject is enrolled in the study.**

a. At baseline visit, DLCO will be repeated after 2nd contrast CT scan

b. At baseline visit, two contrast PVC CT scans will be done. One PVC CT will be done pre-dose and one PVC CT will be obtained 60 minutes post-dose.

***Vitals, height & weight, and urine pregnancy test***

A properly trained member of the study team or UIHC Clinical Research Unit (CRU) employee will perform pre-study vital statistics which include: Heart rate, respirations, blood pressure, temperature, SaO2, height and weight. Women of child bearing potential (WOCBP) will have a urine pregnancy test.

***CO Smokerlyzer***

Subject will be instructed on how the CO Smokerlyzer will be done. Subject will be asked to inhale and hold their breath for the pre-set 15 seconds. A beep will sound during the last 3 seconds of the countdown (on the monitor screen) and following the last beep, the subject will be instructed to blow slowly into the mouthpiece, aiming to empty the lungs completely. %COhb and %fCOhb will be recorded. The subject will be asked to repeat the test again and the results will again be reported. If the results are not <3%, a third test should be performed to ensure repeatability and accuracy.

***Pulmonary function tests***

Complete pulmonary function testing is performed in the PFT lab. All studies conform to American Thoracic Society standards. Both pre- and post- bronchodilator spirometry will be done. Simple spirometry provides FEV1, and FVC and the FEV1/FVC ratio. DLCO will be measured using the single breath carbon monoxide method. Subdivisions of lung volume are measured by body plethysmography. If subjects don't meet the FEV1 and FEV1/FVC GOLD 0-2 criteria, they will be considered screen-fails and will not continue with any other study procedures.

***IV Catheter placement***

Subjects who meet the PFT criteria will be taken to the CRU and CRU nurse, study physician or a properly trained member of the research team will place an IV catheter in the antecubital vein in the subject's right arm. This will be used for contrast injection during the perfused blood volume scans. Blood will also be drawn from the IV catheter for the creatinine, C - reactive protein, cotinine levels and the additional two blood tubes that will be collected for blood and serum analysis at the baseline visit and 90 day visit. Subjects will not have IV catheter placement at any other visits.

### ***Blood and Urine Collection***

Blood samples will be taken to test the subject's creatinine, cotinine and C-reactive protein level. Two additional tubes of blood will be drawn for serum and plasma collection (baseline and 90 day visit). The creatinine level will only be tested prior to the contrast CT (baseline visit and 90 day visit). The cotinine and C-reactive protein level will be tested at baseline, 30 day, 60 day, and 90 day visits. Women of child bearing potential (WOCBP) will have a urine pregnancy test.

### ***CT Scans***

A subject may undergo 13 total low-dose scans throughout the study within 3 months:

**Baseline Visit:** 3 low-dose non-contrast CT volumetric research scans (TLC, FRC, RV) and 2 low-dose dual-energy contrast CT research scans at FRC.

**30-day Visit:** 2 low-dose non-contrast CT Volumetric research scans (TLC, RV)

**60-day Visit:** 2 low-dose non-contrast CT Volumetric research scans (TLC, RV)

**90-day Visit:** 3 low-dose non-contrast CT Volumetric research scans (TLC, FRC, RV) and 1 low-dose dual-energy contrast CT research scan at FRC.

### **Exposure Output**

1. The spiral dual energy contrast scan protocol uses dose modulation with tube A: 120 ref mAs/80kV, tube B: 67 ref mAs/Sn150 kV, with a pitch of 0.55 and rotation time of 0.25sec. The CTDIvol is assumed to be 4.28mGy, with total DLP of 143.2mGy\*cm for a 30cm scan.

Total mrem for three scans: 740 mrem

2. The spiral volumetric scan protocols use dose modulation with 10 reference mAs, 120kV, pitch of 1.0, & rotation time of 0.25sec. The CTDIvol for one scan at 10mAs is 0.67mGy, with total DLP of 22.6mGycm for a 30cm scan.

Total mrem for 10 scans: 1190 mrem

The maximum amount of radiation from the research-related radiation procedures is equivalent to approximately 25% of the annual limit for a radiation worker.

Subjects will wear a pulse oximeter while being scanned.

### ***Smoking Cessation***

Subjects will enter a 3-month smoking cessation program overseen by [name] and [name] who run the hospital-based smoking cessation program. [name] study coordinator will work full time in cooperation with the University of Iowa Hospitals and Clinics Smoking Cessation Clinic in the Pulmonary Rehabilitation Program to maximize success rate. The clinic operates under the Surgeon General's Clinical Practice Guideline Treating Tobacco Use and Dependence: 2008 Update. The study team will meet with the subject in person at the baseline, 30 day, 60 day and 90 day visits and follow up by phone weekly. At the baseline visit the subject will be asked to taper down their use of tobacco for the first week in the study prior to their commitment to quit smoking for the remainder of the study.

Follow up will seek to identify problems already encountered and potential challenges in the immediate future, assessment of current medication use and problems, and restatement of resources to help support them during their tobacco use cessation such as quit-line support.

If tobacco use has occurred, a review of the circumstances and encouragement to recommit to total abstinence will be done.

### ***Randomization***

Subjects will then be randomized to either Sildenafil, 20 mg orally 3x/day, or Placebo in equal numbers after beginning the smoking cessation program above.

### ***Questionnaires***

At baseline, four questionnaires will be administered by the study team:

Human Subject Questionnaire  
Chronic Respiratory Questionnaire  
Baseline Dyspnea Index Questionnaire  
St. George's Respiratory Questionnaire

At the 30 and 60 day visits, two questionnaires will be repeated:

Chronic Respiratory Questionnaire  
Baseline Dyspnea Index Questionnaire

At the 90 day visit, three questionnaires will be repeated:

Chronic Respiratory Questionnaire  
Baseline Dyspnea Index Questionnaire  
St. George's Respiratory Questionnaire

As part of the smoking cessation program, two additional questionnaires are administered:

Fagerstrom Questionnaire  
Tobacco Interview Form

### ***Six Minute Walk***

Subjects will complete a six minute walk test according to the ATS statement (ATS Statement, 2002)

Subjects are encouraged to walk as far as possible for six minutes. Subjects will have heart rate and oxygen saturation (SpO2) measured as well as having their dyspnea rated using BORG scale, prior to and immediately following, the six minute walk.

Subjects will be instructed that they can stop at any time.

The six minute walk will be done at baseline and 90 day visits.

***Safety Monitoring***

A DSMB has been set up with Drs. [name] and [name] as members. Members will be provided summary data on a 6-month basis.

Image Quantitation and Outcome Measures: Lung density histogram-based measures of parenchymal characteristics and PBV parameters extracted using the Siemens software for material decomposition will serve as the primary metrics in this project. Regional PBV will be expressed as a percent of the total lung PBV. The primary outcome measure in this study will be CV of PBV and regional ventilation along with neutrophil accumulation assessed by SPECT. The primary measure used to assess lung parenchyma in the non-contrast scans will be the percent of lung falling below -950 HU. Secondary measures include the position of the lower 15th percentile point on the lung density histogram (P15) and “Alpha” negative of the slope of the log-log plot of the number of holes plotted against hole size (44) with holes defined as connected voxels < -950 HU. In all of the volume scans we will extract the lungs, lobes, sub-lobe segments, airway tree out to two generations beyond the segmental airways as outlined in (1) in addition to assessing CV of PBV and ventilation (from image matching) and lung density measures for completeness of lung characterization. From the image matching, we will have lung density on a region-by-region basis at an acinar level of detail. Based upon density changes within a known regional volume of lung, we have a measure of regional ventilation. In the Sildenafil study, change in DLCO (pre and post Sildenafil) will serve as a secondary outcome measure with the expectation that as inflamed lung regions are perfused, DLCO will drop but that this will recover in the smoking cessation follow-up and will correlate with a drop in total lung density on the TLC scans. In addition to evaluating CV of PBV and ventilation, we will warp pre and post hypoxia and Sildenafil PBV image sets and test whether the regions of highest PBV remain high under hypoxia in the emphysema susceptible smokers and whether the regions of low PBV increase with Sildenafil. This test will significantly strengthen the link back to our primary hypothesis. Image matching software developed in house (53, 55-59) will be used to correlate data from the non-contrast volume scan and the PBV DECT scan. Heterogeneity of PBV will be assessed using our in-house PASS software. All other analysis will be assessed via VIDA’s (Software derived from our laboratory and now commercialized and FDA 510K cleared) Apollo software. The VIDA software together with PASS has analyzed over 50,000 CT data sets from a growing number of multi-center investigations. Details of analysis approaches are given in (1). Segmentation results are passed between Apollo and PASS. In PASS, we are able to use the vascular tree extracted by Apollo to identify the vascular paths that serve to define the sub-lobe segments. We will use these lobar and sub-lobe demarcations as the basis for evaluating PBV heterogeneity and lung density metrics in the emphysema susceptible and emphysema-free normal smokers.

Statistical Analysis

For outcome variables that meet a normal distribution error assumption (or are suitable to normalization through a transformation) our statistical analysis for Aims 1-4 will be primarily based on general linear models with identity link and normality of errors. Specifically, we will look at increasing/decreasing trends of the outcome variable as well as pair-wise comparisons across groups. These pair-wise comparisons will be obtained as orthogonal contrasts within the linear models. For those variables that do not meet the assumptions of the general linear models

we will use generalized additive models (GAM). These regression models allow for exploration of nonparametric relationships of an outcome variable with a number of independent variables simultaneously and identify associations when the response variable is not normally distributed or equal variance assumptions are not met. PBV measures will also be assessed using Bland-Altman methods, with adjustment for heteroscedasticity if present. For comparisons that involve an intervention (e.g., hypoxia and Sildenafil), differences between study groups will be estimated by a time (pre/post)*group interaction term in linear models with generalized estimating equations.

All models will be adjusted for covariates. Covariates will be considered for inclusion into regression models based principally on plausible evidence and secondarily on evaluation of statistical associations in the dataset. Data from multiple scans of the lung of a subject are generally spatially and/or temporally correlated; we will account for such correlation in the analysis, e.g. as random effects in a linear mixed model (113) Since a major interest in this study is to investigate differences between ordinal groups we perform pair wise comparisons between groups. To control the experiment-wise type I error (“multiple comparisons”), we use the Holm step-down procedure, an improved version of the Bonferroni criterion. Subject dropout and resultant missing data in the smoking cessation project will use the Generalized Estimating Equation GEE to impute the missing values for our generalized linear model analysis of the data.

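### No carboxyhaemoglobin correction of DLCO is specified, so CO clearance in subjects who quit can mimic the recovery that the SAP expects by day 90

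*SAP*

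**What the plan says.** **Outcome.** In the SAP, Image Quantitation and Outcome Measures, "change in DLCO (pre and post Sildenafil) will serve as a secondary outcome measure". The expected course is that "DLCO will drop but that this will recover in the smoking cessation follow-up", and the recovery is expected to correlate with a fall in total lung density on the TLC scans. The SAP attributes the fall to perfusion of inflamed lung.

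**Measurement.** In the protocol, Pulmonary function tests, "DLCO will be measured using the single breath carbon monoxide method". The same section says "All studies conform to American Thoracic Society standards". The Schedule of Study Assessments and Procedures places pulmonary function tests at baseline and day 90. Its footnote adds: "At baseline visit, DLCO will be repeated after" the second contrast CT, which is taken 60 minutes after a dose.

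**CO exposure.** Subjects smoke at least half a pack a day at entry (Inclusion/exclusion criteria). All are asked to taper in week 1 and then quit (Smoking Cessation). Under CO Smokerlyzer, "COhb and %fCOhb will be recorded". The schedule row "Exhaled CO Smokerlyzer" is marked once for each of the baseline, 30, 60 and 90 day visits.

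**Analysis.** The SAP, Statistical Analysis, estimates intervention effects, naming sildenafil, by a time-by-group interaction with GEE. Covariates are to be chosen mainly on plausibility. COHb is not named, and no COHb correction of DLCO appears in the protocol or SAP text available.

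**The concern.** CO already bound in the blood reduces CO uptake in the test, so measured DLCO depends partly on recent smoking and recent CO tests. That dependence can run in the direction the SAP predicts. CO inhaled during the first baseline test could lower the same-day repeat, and CO clearance in quitters can raise the day-90 value. Neither step needs a drug effect.

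Two readings of the data are exposed. One is a within-arm drop and recovery taken as evidence of mechanism. The other is the subject-level correlation between DLCO recovery and falling lung density. If density also falls with quitting, quitters will tend to show both changes, and COHb clearance supplies part of the DLCO change. Randomisation does not protect that correlation. Uneven quitting could also add a small bias to the arm comparison, and the spread between quitters and non-quitters adds noise.

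**Working it through.** The documents give no effect size, SD or quit rate for DLCO, so there is no planned figure to reproduce. From the documents: 80 subjects randomised equally, hence 80 / 2 = 40 per arm. **Every other input below is an assumption.**

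**1. Rise in DLCO in one quitter.** Coefficient (% of DLCO per COHb point) × COHb fall (points).
- Central: 1.0 × 4 = 4%.
- Range: 0.5 × 2 = 1% to 1.5 × 6 = 9%.

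**2. Mean rise in an arm.** Step 1 × proportion quitting.
- Central, 30% quitting: 4% × 0.30 = 1.2%.
- Range, 10% to 50% quitting: 0.5 × 2 × 0.10 = 0.1% to 1.5 × 6 × 0.50 = 4.5%.

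**3. Bias in the arm difference.** Step 1 × difference in quit rate. With a 20-point gap:
- Central: 4% × 0.20 = 0.8%.
- Range: 1% × 0.20 = 0.2% to 9% × 0.20 = 1.8%.
- With an SD of change of 6%, the standard error of the arm difference is 6 × √(2/40) = 1.34%, so the central bias is 0.8 / 1.34 = 0.6 standard errors.

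**4. Added noise at 30% quitting.** SD from the quitter/non-quitter mix = 4 × √(0.3 × 0.7) = 1.83%, variance 3.36. Relative to an SD of change of 8% this adds 3.36 / 64 = 5% to the variance; relative to 4%, 3.36 / 16 = 21%.

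**5. Same-day change in COHb.** Gain = points per manoeuvre × manoeuvres. Loss = starting COHb × (1 − 0.5^(hours / 5)), taking a 5-hour half-life.
- Lowest: 0.3 × 2 − 6 × (1 − 0.5^(3/5)) = 0.60 − 2.04 = −1.4 points.
- Highest: 0.8 × 6 − 3 × (1 − 0.5^(1.5/5)) = 4.80 − 0.56 = +4.2 points.

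The sign is not fixed, because the number of manoeuvres and the time between tests are not stated.

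**6. False-positive rates with no drug effect.** Simulation of 20,000 trials per setting, 40 per arm, two-sided 0.05, SD of change 4% to 8%, 1% of DLCO per COHb point. It compares a one-sample t-test on change within an arm with a two-sample t-test on change, the simple equivalent of the time-by-group term.

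| Setting | Within arm | Between arms |
|---|---|---|
| Same-day shift of −1% to −3%, equal in both arms | 11% to over 99% | about 5% |
| Day 90, 30% quit in both arms, COHb fall 4 or 6 points | 15% to 63% | about 5% |
| Day 90, 50% vs 30% quit, COHb fall 4 or 6 points (bias 0.8% or 1.2%) | 32% to 96% | 7% to 19% |

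**7. What the recorded COHb can correct.** Baseline and day 90 each have a reading, so that change can be corrected. The two same-day baseline tests share one reading. A percentage correction multiplies both by the same factor c, and (c × second) / (c × first) = second / first, so the percentage change is untouched.

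**The case against.** The strongest defence is that the trial is randomised and the time-by-group contrast removes any CO effect shared by the arms. The simulation bears this out: the contrast keeps its 5% level when quitting is balanced, and all subjects receive the same cessation programme. A 20-point quit-rate gap has no basis in the documents, and even then the central bias is well under one standard error. This stands, provided that group means randomised arm. The SAP does not define the term, and elsewhere it compares emphysema-susceptible with emphysema-free smokers. The defence does not reach within-arm readings or the density correlation.

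It can also be said that ATS conformity and the covariate rule leave room for a correction. That is fair as far as it goes: the laboratory may adjust for COHb. But neither statement says whether the analysed DLCO is adjusted, or how.

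A reader might infer more: that DLCO is definitely uncorrected, that a lower second baseline value is to be expected in both arms, or that the sildenafil comparison is invalid. The documents support none of these. They are silent on correction, the same-day direction is uncertain, and the arm contrast is valid under balance. Nor can it be assumed that a placebo contrast exists at 60 minutes. The schedule footnote says only that a dose is given, and Randomization places allocation after the cessation programme begins.

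**Conclusion.** The point holds as a gap in specification for a secondary outcome. CO clearance can account for some or all of a within-arm DLCO recovery by day 90: about 4% in a quitter (range 1% to 9%), or 1.2% averaged over an arm with 30% quitting (range 0.1% to 4.5%). It can also contribute to the correlation with falling density. A same-day drop from test CO is possible but not established. The randomised contrast is affected only if quitting or CO exposure differs by arm, by about 0.8% of DLCO (range 0.2% to 1.8%) for a 20-point quit-rate gap. All these sizes rest on assumed coefficients, COHb falls and quit rates. The absence of a stated correction and the once-per-visit reading come from the documents.

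**What to change.** 1. In the SAP, define the baseline-to-day-90 DLCO outcome as DLCO corrected for the %COHb recorded at the same visit. Name the correction formula, and state that the breath reading is taken before the DLCO test. Report uncorrected DLCO as a sensitivity analysis.
2. Use corrected DLCO in the correlation with lung density.
3. Define group in the time-by-group model as randomised arm, and rest drug-effect conclusions on that contrast, not on a within-arm drop and recovery.
4. For the same-day change, either repeat the Smokerlyzer test before the post-dose DLCO and correct each value with its own reading, or state that the within-arm same-day change will not be interpreted as a drug effect.
5. Reconcile the schedule footnotes with Randomization on whether the baseline dose is the randomised product.

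Items 1 to 3 cost SAP wording and one calculation on data already scheduled for collection. Item 4 costs one further brief breath test at baseline if the first option is taken. Item 5 is a clarification of the protocol.

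### Does the supportive test of whether low-PBV regions rise with sildenafil lack a comparator, so that a rise would appear without any drug effect?

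*SAP*

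**What the plan says.** The SAP, under Image Quantitation and Outcome Measures, states that "we will warp pre and post hypoxia and Sildenafil PBV image sets" and will then test "whether the regions of low PBV increase with Sildenafil. This test will significantly strengthen the link back to our primary hypothesis". On scale, "Regional PBV will be expressed as a percent of the total lung PBV", so a gain in one region is matched by a loss elsewhere. The sentence gives no cut-off for low, does not say which scan defines it, and mentions no comparison arm.

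The SAP's Statistical Analysis section gives a general rule. For comparisons that involve an intervention, with sildenafil named as an example, "differences between study groups will be estimated by a time (pre/post)*group interaction term in linear models", fitted with generalized estimating equations.

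The Protocol supplies the design. Under Randomization: "Subjects will then be randomized to either Sildenafil, 20 mg orally 3x/day, or Placebo in equal numbers after beginning the smoking cessation program above". A note to the Schedule of Study Assessments and Procedures says of the baseline visit: "One PVC CT will be done pre-dose and one PVC CT will be obtained 60 minutes post-dose". One further contrast scan is taken at 90 days. Under Smoking Cessation, every participant tapers tobacco use in the first week, "prior to their commitment to quit smoking for the remainder of the study".

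**The concern.** Read alone, the sentence describes a before-and-after change in regions chosen because they were low. If the choice is made on the pre scan, some regions are low partly through measurement error that will not repeat, so they rise on the next scan even if the drug does nothing. By day 90 every participant has also been asked to stop smoking, so a change within one arm would mix drug and cessation. The SAP intends to use this result as support for its main hypothesis, so a rise produced by the selection rule could be read as a sildenafil effect. The primary outcome, the coefficient of variation (CV) of PBV, does not depend on this test.

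**Working it through.** **Inputs.** The Protocol's Overview gives 80 participants. Equal allocation makes 80/2 = 40 per arm. The documents give no scan-rescan reliability r, between-region CV, number of regions, cut-off or alpha level. The following are assumed: r from 0.70 to 0.999, observed between-region CV 0.30, the lowest 20% of regions called low, independent normal errors, two-sided alpha 0.05. The plan gives no figure of its own to reproduce.

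**1. Expected rise with no drug effect, regions picked on the pre scan.** In SDs of observed regional PBV, rise = (1 − r) × φ(z_q)/q. For q = 0.20, φ(z_q)/q = 0.280/0.20 = 1.40. Multiplying by CV 0.30 gives the rise as a share of mean regional PBV.

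- r = 0.70: 0.30 × 1.40 = 0.42 SD, or 12.6%
- r = 0.90: 0.10 × 1.40 = 0.14 SD, or 4.2%
- r = 0.95: 0.05 × 1.40 = 0.07 SD, or 2.1%
- r = 0.99: 0.01 × 1.40 = 0.014 SD, or 0.4%

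**2. How often each test would mislead.** Null simulation, 1,000 trials per setting, PBV rescaled to percent of total. The one-arm test is a one-sample t-test counted when significant and upward (nominal 2.5%).

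| Regions | r = 0.70 | 0.90 | 0.95 | 0.99 | 0.999 |
|---|---|---|---|---|---|
| 5 | 89% | 43% | 25% | 7% | 3% |
| 20 | 100% | 98% | 80% | 25% | 7% |
| 100 | 100% | 100% | 100% | 85% | 17% |

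In the same trials, the two-sample comparison of change between arms rejected in 3.7% to 6.5% (nominal 5%).

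A second simulation used anatomical units: the lowest 4 of 18 segments, or the lowest of 5 lobes. At r = 0.80, 0.90, 0.95, 0.98 and 0.99, false one-arm rises occurred in about 100, 98, 80, 41 and 24% of trials (segments) and 72, 43, 24, 13 and 8% (lobes). The between-arm test stayed at about 4 to 6%.

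With 20 regions picked on the average of the two scans, the one-arm rate fell to 2.2% to 2.5%. The artefact therefore depends on a selection rule that the SAP does not state.

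**3. Why the between-arm contrast is safe.** Let B be the rise due to selection, C the mean change due to the cessation programme, and δ the drug effect. Expected change is B + C + δ on sildenafil and B + C on placebo, so the interaction estimates δ. B is equal in the two arms because selection on a pre-treatment scan cannot depend on allocation. C is equal because both randomised arms follow the same programme.

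**4. Which contrast the plan prescribes.** The Statistical Analysis rule names sildenafil and calls for a difference between groups in pre/post change. The Protocol describes one cohort of current smokers and divides it only into sildenafil and placebo. Together these give the contrast in step 3. No passage specifies a one-sample test within the sildenafil arm.

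**5. Price of that contrast.** With SD of change σ, the standard error is σ/√40 = 0.158σ within one arm and σ√(2/40) = 0.224σ between arms, a ratio of 1.41. The difference detectable with 80% power is (1.960 + 0.842) × 0.224 = 0.63 SD of change, before dropout. The randomised design already carries this cost.

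**The case for a change.** The strongest case for a change is that nothing in the regional sentence invokes the interaction. The available SAP text never mentions placebo, and the groups it names alongside PBV are smokers with and without susceptibility to emphysema. If group meant those phenotypes, the interaction would not separate drug from cessation. The matching hypoxia clause is also worded as a within-subject comparison. Further, the 60-minute scan gives a placebo contrast only if the baseline dose is the randomised treatment, which the Protocol does not state outright.

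Part of this stands. The link between sentence and rule, the meaning of group and the selection rule are all unwritten in the text available, although one part of the SAP could not be consulted and the SAP refers to a cited source for analysis details. The phenotype reading is weak here. The Statistical Analysis section speaks of Aims 1-4 while the Protocol covers Aim 5, so the SAP wording is shared with other studies. Within the sentence, the susceptible smokers qualify the hypoxia half and not the sildenafil half.

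On the 60-minute scan, the Schedule places cessation enrolment and dispensing of medication or placebo at the baseline visit. This fits randomisation after the programme begins, so it is an omission and not a contradiction. If pre and post mean the two baseline scans, the cessation argument also falls away, because nobody has yet been through the programme.

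**Conclusion.** The concern does not call for a change. The artefact is real for a one-arm test on regions picked from the pre scan: a false rise in 25% to 100% of trials at reliability 0.90 to 0.95 for 20 or more regions or for five (25% to 43% for five alone), all on assumed inputs. That test is not in the plan. The analysis that the Statistical Analysis section assigns to sildenafil comparisons, applied to the only groups this trial has, keeps the error rate near 5% under any rule for choosing low regions on the pre-treatment scan.

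The conclusion rests on three readings: group means randomised arm, the regional test follows the stated interaction, and low regions are chosen by one rule applied alike in both arms. An analyst of this trial would adopt all three without instruction. If a report nevertheless presented a rise within the sildenafil arm alone, it should not be read as a drug effect. That would be a fault in the report, on a supportive test, and would leave the primary outcome as it is.
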